9.3.1.2. Secondary Outcomes

- Description of subtypes of AML and B-cell ALL based on the cytogenetic and molecular abnormalities, according to the WHO classification.
- Proportion of patients of each prognostic-risk group (favorable, intermediate, adverse) among newly diagnosed AML patients, based on cytogenetic profile
- Description of the treatment standard from diagnosis to inclusion of R/R ALL patients.
- Description of clinically relevant events presented by AML and relapsed/refractory B-cell ALL patients since treatment initiation until loss of follow-up or death from any cause.
- The EFS will be the measure of time since treatment initiation until failure to achieve complete remission (CR), or disease progression after CR, or death from any cause for both AML and relapsed/refractory B-cell ALL patients.
- The OS will be the measure of median time since treatment initiation until death from any cause for both AML and relapsed/refractory B-cell ALL patients.
- The OS will also assess the proportion of AML and relapsed/refractory B-cell ALL patients alive after 1, 3 and 5 years since treatment initiation.
- For AML patients who achieved CR, the RFS will be the measure of time since the CR attainment until relapse or death from any cause.
- For AML patients the response to induction and consolidation therapy will assess the proportion of patients who achieve complete remission (CR), complete remission with incomplete hematological recovery (CRI), complete remission without minimal residual disease (MDR-), partial remission (PR), and progressive disease.
- For relapsed/refractory B-cell ALL patients the response to the rescue treatment will assess the proportion of patients with complete remission (CR), complete remission without minimal residual disease (MRD-), partial remission (PR), and progressive disease.

- Heath care resource utilization description, considering the outpatient utilization, inpatient admissions, hospitalization length of stay, and concomitant medication prescription since diagnosis until the loss of follow-up or death from any cause.

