8.3.2. Outcomes

Primary outcomes

1. Description of demographic and clinical presentation characteristics at the moment of R/R B-cell ALL or AML diagnosis
2. Treatment description considering the front-line therapy and subsequent regimen(s) required for patients with R/R B-cell ALL and AML, including any systemic chemotherapy, target therapy, hematopoietic stem cell transplantation (autologous/allogenic), intrathecal chemotherapy and palliative management.

Secondary outcomes

3. Description of subtypes of AML and B-cell ALL based on the cytogenetic and molecular abnormalities, according to the WHO classification

Effective Date: 01Feb2022

4. Proportion of patients of each prognostic-risk group (favorable, intermediate, adverse) among newly diagnosed AML patients, based on cytogenetic profile
5. Description of the treatment standard from diagnosis to inclusion of R/R ALL patients
6. Description of clinically relevant events presented by AML and R/R B-cell ALL patients since treatment initiation until loss of follow-up or death from any cause;
7. The EFS will be the measure of time since diagnosis until failure to achieve complete remission (CR), or disease progression after CR, or death from any cause for both AML and R/R B-cell ALL patients;
8. The OS will be the measure of median time since diagnosis until death from any cause for both AML and R/R B-cell ALL patients;
9. The OS will also assess the proportion of AML and R/R B-cell ALL patients alive after 1, 3 and 5 years, if feasible, since treatment initiation;
10. For AML patients who achieved CR, the RFS will be the measure of time since the CR attainment until relapse or death from any cause;
11. For AML patients the response to induction and consolidation therapy will assess the proportion of patients who achieve CR, complete remission with incomplete hematological recovery (CRI), complete remission without minimal residual disease (MDR-), partial remission (PR), and progressive disease
12. For R/R B-cell ALL patients the response to the rescue treatment will access the proportion of patients with CR, complete remission without MRD-, PR, and progressive disease
13. Health care resource utilization description, considering the outpatient utilization, inpatient admissions, hospitalization length of stay, and concomitant medication prescription since diagnosis until the loss of follow-up or death from any cause.

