- Relapse-free survival (RFS) for newly diagnosed AML patients – considered as the date of achievement of a remission until the date of relapse or death from any cause; patients not known to have relapsed or died at last follow-up are censored on the date they were last examined, study enrollment, last contact, whichever comes later. Defined only for patients achieving CR, or CRI. The RFS will be measured as the treatment end date until next treatment initiation or date of death, whichever comes first, for all AML patients who achieved Complete remission/response (CR) or Complete remission/response with incomplete hematological/count recovery (CRI) at the end of treatment.
- Event-free survival (EFS) of newly diagnosed AML and R/R B-cell ALL patients – considered as the date of initiation of treatment (or date of diagnosis, if the previous is not available) to the date of primary refractory disease, or relapse from CR, or CRI, or death from any cause; patients not known to have any of these events are censored on the date they were last examined, study enrollment, last contact, whichever comes later. The EFS will be measured as the time since AML and R/R ALL initiation of treatment (or newly AML diagnosis and newly ALL diagnosis, if treatment date is not available) until i) treatment end date (or treatment start date of the next treatment line, if the previous is not available) when treatment response was Refractory disease(5) or Relapsed from CR or CRI or recurrent disease(6) as treatment response; ii) date of death, whichever comes first.
 - Clinically relevant events:
 - Hematological toxicities
 - Hepatotoxicity
 - Gastrointestinal toxicities
 - Tumor lysis syndrome
 - Fatigue
 - Dysgeusia
 - Alopecia
 - Muscle spasms
 - Infections

- Sepsis
- Secondary malignancy due to drug toxicity
- Death
- Other

Medical Dictionary for Regulatory Activities Terminology (MedDRA) version 2.1 (V2.1) or newer version will be used as a standardised medical terminology. Medicinal product names will be codified using World Health Organisation Drug Dictionary (WHODrug), a dictionary maintained and updated by Uppsala Monitoring Centre (UMC).

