 - Hepatotoxicity.
- Most common adverse events description

7. To each newly AML and R/R B-cell ALL patients, the EFS will measure time since the date of initiation of treatment (or newly AML diagnosis and newly ALL diagnosis, if the previous is not available) until i) treatment end date (or treatment start date of the next treatment line, if the previous is not available) when treatment response was Refractory disease(5) or Relapsed from CR or CRI or recurrent disease(6); i) date of death, whichever comes first. This time-to-event analysis will be described summarized in tables and using Kaplan Meier methods and plot, if appropriate. Patients not known to have any of these events are censored on the date they were last examined:

newly AML

- Descriptive (median and CI(95%) estimations of Kaplan-Meier) of EFS;
- Time categorized count and percentages.

R/R B-cell ALL

- Descriptive (median and CI(95%) estimations of Kaplan-Meier) of time between treatment initiation and R/R event in months;

- Time categorized count and percentages.

8. The OS will be measure for both newly AML and R/R B-cell ALL patients as median time since newly diagnosis or treatment initiation until death from any cause. This time-to-event analysis will be described using a Kaplan Meier plot, if appropriate

newly AML

- Descriptive (median and CI(95%)) estimations of Kaplan-Meier) of time between date of diagnosis or treatment initiation and R/R event in months;
- Time categorized count and percentages.

This analysis will also be described for fit and non-fit newly AML patients.

R/R B-cell ALL

- Descriptive (median and CI(95%)) estimations of Kaplan-Meier) of OS;
- Time categorized count and percentages.

9. The median OS and the percentage (and 95% confidence intervals) of alive patients in 1, 3- and 5-years, if feasible, follow up of newly diagnosed or treatment initiation AML and R/R B-cell ALL patients will be assessed. The OS will be defined as median time since newly diagnosis or treatment initiation until death from any cause. This time-to-event analysis will be described using a Kaplan Meier plot, if appropriate.

newly AML

- Descriptive (median and CI(95%)) estimations of Kaplan-Meier) of time between treatment initiation and death in months;
- Time categorized count and percentages.

This analysis will also be described for fit and non-fit newly AML patients

R/R B-cell ALL

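### The Kaplan-Meier output line for EFS in R/R B-cell ALL leaves out death, against the SAP's own definition, and the item 8 output line for AML overall survival carries the same misplaced endpoint

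*SAP*

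**What the plan says.** SAP 8.7.2 item 7 opens with one EFS definition for both cohorts: "To each newly AML and R/R B-cell ALL patients, the EFS will measure time since the date of initiation of treatment". The interval ends at a treatment response coded as refractory or as relapsed/recurrent, or at the "date of death, whichever comes first. This time-to-event analysis will be described summarized in tables". The censoring rule follows: "Patients not known to have any of these events are censored on the date they were last examined".

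The output lists under that text differ by cohort. For newly diagnosed AML the line is "Descriptive (median and CI(95%) estimations of Kaplan-Meier) of EFS". For R/R B-cell ALL it is "estimations of Kaplan-Meier) of time between treatment initiation and R/R event in months".

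The definitions elsewhere include death:
- SAP 8.7 runs EFS "to the date of primary refractory disease, or relapse from CR, or CRI, or death from any cause". Protocol 9.7 has the same event list.
- SAP 8.3.2, outcome 7, ends with "or disease progression after CR, or death from any cause for both AML and R/R B-cell ALL patients".
- Protocol 9.3.1.2 ends with "or disease progression after CR, or death from any cause for both AML and relapsed/refractory B-cell ALL patients".

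Item 8 of SAP 8.7.2 covers overall survival (OS), and its lead text ends the interval at death. Its R/R B-cell ALL line names OS, but its newly diagnosed AML line ends the interval at an R/R event.

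**The concern.** EFS in R/R B-cell ALL is a named secondary objective (Protocol 8.2, SAP 7.2), and the line in question is the only Kaplan-Meier line listed for it under item 7. Output lines in this section are not always mere labels. Item 9, for example, spells out the start and stop of the clock for its survival outputs. A programmer could therefore take the ALL line of item 7 as the operational specification and count only R/R events.

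The deaths lost that way would not all be picked up by a response code:
- Protocol 9.2.3 leaves deaths in aplasia and deaths of indeterminate cause out of refractory disease.
- Item 7 triggers on the refractory and relapsed/recurrent codes, while item 12 lists progressive disease as a separate response. A patient coded as progressive who then dies, with no other line coded refractory or relapsed, has an EFS event only through death.

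The phrase is also unclear in this cohort, because every ALL patient is relapsed or refractory at entry. Where the treatment start date is missing, SAP 8.7 and item 7 fall back to the newly ALL diagnosis. From that origin an R/R event could be taken to mean the one that made the patient eligible.

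**Working it through.** The plan states no EFS figure, event rate or sample-size calculation, so there is no figure to reproduce. The check is a comparison of texts, followed by an illustration of size.

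**Step 1: is death an event?**

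| Place | Cohort | Death counted? |
|---|---|---|
| Protocol 9.3.1.2, EFS | AML and ALL | Yes |
| Protocol 9.7, EFS | AML and ALL | Yes |
| SAP 8.3.2, outcome 7 | AML and ALL | Yes |
| SAP 8.7, EFS | AML and ALL | Yes |
| SAP 8.7.2 item 7, lead text | AML and ALL | Yes |
| SAP 8.7.2 item 7, AML output line | AML | Yes, by naming EFS |
| SAP 8.7.2 item 7, ALL output line | ALL | **Not named** |
| SAP 8.7.2 item 8, lead text (OS) | AML and ALL | Yes |
| SAP 8.7.2 item 8, ALL output line (OS) | ALL | Yes, by naming OS |
| SAP 8.7.2 item 8, AML output line (OS) | AML | **Not named** |

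The definitions differ in other respects (SAP 8.3.2, for instance, starts EFS at diagnosis), but they agree on death. The two exceptions are both output lines, both use the R/R event wording, and they mirror each other: the ALL line in item 7, the AML line in item 8.

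**Step 2: size if the item 7 ALL line were programmed literally with deaths censored.**

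Assumptions, none of them from the documents: constant hazards, independent causes, true median EFS m, and a share d of first events that are deaths.

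- Total first-event hazard: h = ln 2 / m.
- Hazard of an R/R event alone: h(1-d).
- Median with deaths censored: ln 2 / [h(1-d)] = m/(1-d). The inflation factor is 1/(1-d), whatever m is.
- 12-month value with deaths censored: exp[-12h(1-d)], which is the true 12-month EFS raised to the power (1-d).

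With an assumed m of 6 months, h = 0.693/6 = 0.1155 per month and true 12-month EFS is exp(-12 × 0.1155) = 25%.

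| d | 1/(1-d) | Median, months (true 6) | 12-month value (true 25%) |
|---|---|---|---|
| 10% | 1.11 | 6.67 | 28.7% |
| 20% | 1.25 | 7.50 | 33.0% |
| 30% | 1.43 | 8.57 | 37.9% |
| 40% | 1.67 | 10.0 | 43.5% |

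Kaplan-Meier medians from 200,000 simulated patients per row were 6.66, 7.49, 8.59 and 9.97 months, in agreement with the formula.

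**Step 3: the item 8 AML line.** Read literally, it ends at relapse or refractory disease, and a death without either is no event. Ending at relapse shortens the time and ignoring deaths lengthens it, so the documents do not fix the direction of the error. The result would not be survival.

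**Step 4: the start date.** SAP 8.7 starts EFS at the initiation of treatment for R/R ALL, which suits this cohort. Only the fallback departs from it. SAP 8.2.2 sets the index date at the first diagnosis of R/R B-cell ALL, whereas the fallback uses the earlier, original ALL diagnosis.

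**The case against.** The strongest reply is that the governing text is already right. Item 7's lead text, two other places in the SAP and two in the protocol count death, and item 7 censors only patients with none of the listed events, of which death is one. A reader might infer from the output line that ALL EFS is overstated, or that ALL deaths must be censored. The documents do not support either inference: no passage says that ALL deaths are censored, and the bias arises only if someone follows one line against five consistent definitions.

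The same wording in the item 8 AML line also points to a misplaced phrase and away from a deliberate death-free endpoint. For AML survival, item 9 separately asks for the median time from treatment initiation to death, so a correct output is specified there in any case.

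A reader might also infer that AML and ALL results are made non-comparable. That is a limited matter. SAP 8.2.5.3 has no comparator, SAP 8.7 tests no hypothesis, and the cohorts are newly diagnosed AML and R/R ALL. What remains is that two unlike endpoints could sit under one heading.

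All of this stands, and it makes the harm conditional. It does not make the two lines correct. The table shells, which might show what is intended, are an attached file (SAP 13.1) whose content is not in the text.

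**Conclusion.** The item 7 output line for R/R B-cell ALL is wrong as written: it omits an event that every definition of the endpoint includes. The item 8 output line for newly diagnosed AML is wrong in the same way. The likely cause is a drafting error.

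The consequence depends on programming. If the ALL line is followed literally with deaths censored, ALL EFS is biased upward. For d between 10% and 40% the median is inflated by 11% to 67%, under constant and independent hazards. The range of d and the 6-month median are illustrative and say nothing about what this cohort will show. If the lead text is followed, there is no bias. The point deserves correction because it concerns a named secondary objective and the text leaves the choice to whoever programs the table.

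**What to change.** 1. In SAP 8.7.2 item 7, change the R/R B-cell ALL line to the Kaplan-Meier median and 95% CI of EFS, running from initiation of treatment for R/R ALL to refractory disease, relapse or death from any cause.
2. In item 8, change the newly diagnosed AML line to the Kaplan-Meier median and 95% CI of OS, with death from any cause as the event.
3. In SAP 8.7 and item 7, reconcile the 'newly ALL diagnosis' fallback start for the R/R ALL cohort with the R/R index date in SAP 8.2.2.
4. Check the table shells against these definitions.

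Time to the next relapse or refractory event could be reported separately, as a cumulative incidence with death as a competing event, but no stated objective requires it.

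The cost is two output lines, one clause on the fallback date and a shell check. Reported ALL EFS may be shorter than under a literal reading of the present line.

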8.7.3. Multivariate Analysis by Objective

Not applicable

8.7.4. Adjustment for Confounding

If possible, the following adjustment for confounding will be performed according to the data availability:

- age
- country
- cytogenetic risk
- ECOG performance status

8.7.5. Effect Modification

Not applicable

8.7.6. Sub-group Analysis

Sub-group analyses will be conducted as stated in the analysis sections. It should be noted that the study was not designed to detect treatment differences within sub-groups. The following sub-groups will be assessed according to the data availability and described within the analysis sections, as appropriate:

Upon availability of data, primary objectives (clinical and demographics characteristics, and treatment patterns) and survival secondary objectives (EFS, OS, RFS) analysis will be stratified by the:

- ECOG
 - 0-1
 - 2-5
- cytogenetic risk

Effective Date: 01Feb2022

- newly AML: favourable, intermediate and poor/adverse
- R/R B-cell ALL: good prognosis, intermediate prognosis, poor prognosis and undetermined prognosis
- country
 - Argentina,
 - Brazil
 - Chile
 - Colombia
- age range
 - \leq 39 years old at diagnosis
 - 40 – 64 years old at diagnosis
 - \geq 65 years old at diagnosis

8.7.7. Missing Data

Missing values will be included in the denominators for the calculation of percentages and missing categories will be presented. In general, missing data will not be imputed, and the data will be analyzed as they are recorded in the study CRFs. However, if more than 10% of data is missing for one or more key variables, the impact of missing data on the analysis will be discussed, and the pattern of missing data may be explored. If there is evidence of bias in the missing data, and variables that are considered good predictors of the missing data are available, the multiple imputation method at the study level may be used to replace missing values as secondary exploratory analyses. If the multiple imputation method is used, a sensitivity analysis will be carried out comparing results from the complete case analysis (where records with missing data will be dropped) and the full set analysis (with imputed data). Another potential strategy is a mixed-effects model repeated measures analysis. This approach helps to conserve patient data in the event of missing observations. It is also potentially advantageous in registry studies with often irregularly spaced clinic visits and observations.

8.7.8. Pooling and Meta-Analysis

Not applicable

8.8. Limitations of the Statistical Analysis

Data collected from source documentation and entered into the electronic CRF will be described. No imputation for missing data will be conducted. The loss to follow-up, including patients early discontinuing the treatment, the transference of treatment institution, or patients for whom the death was not documented in their chart, consists of an intrinsic limitation of the retrospective study design.

8.9. Quality Control

IQVIA Quality Management System (QMS)

At the study level, all aspects of the study from protocol development to the reporting of the results are conducted within the work-frame of IQVIA Quality Management System (QMS) and in accordance with the global procedure RWI_OP_BIOS0006RW: Biostatistics for Non-Interventional Studies and Low Intervention Clinical Trials, and RWI_WI_BIOS0021: Biostatistics Quality Control for Analysis Datasets and Statistical Output, which include quality control on study methodology, statistical analysis plan, programming, data management and analysis, study results, conclusions and study report.

9. Protection of Human Subjects Related to the Analysis

This research presents no more than minimal risk of harm to patients and involves no physical procedures with patients, therefore, a waiver of informed consent will be requested as only retrospective collection of anonymized, non-personally identifiable data will be performed. Alternatively, patients will be informed accordingly, and will be asked to give their consent on data handling procedures in accordance with national regulations in place in each of the countries included in the study.

All data will be extracted from patient's medical chart and entered into an electronic CRF specifically designed to capture relevant information in accordance with the study outcomes. Prior to the enrolment of any patient, the study must be evaluated by the local independent ethics committees (IEC) and/or institutional review board (IRB) and a formal approval must be provided.

10. Management and Reporting of Adverse Events/ Adverse Reactions

Pursuant to the European Medicines Agency (EMA) requirements for reporting of adverse events for secondary data (GVP module VI, VI.C.1.2.1.2), adverse event reporting will not be conducted as part of this study given the study objectives will be met through the use of secondary data.

This study requires human review of patient-level unstructured data; unstructured data refer to verbatim medical data, including text-based descriptions and visual depictions of medical information, such as medical records, images of physician notes, neurological scans, X-rays, or narrative fields in a database. The reviewer is obligated to report adverse events (AEs) with explicit attribution to any Pfizer drug that appear in the reviewed information (defined per the patient population and study period specified in the protocol). Explicit attribution is not inferred by a temporal relationship between drug administration and an AE but must be based on a definite statement of causality by a healthcare provider linking drug administration to the AE.

The requirements for reporting safety events on the non-interventional study (NIS) adverse event monitoring (AEM) Report Form to Pfizer Safety are as follows:

- All serious and non-serious AEs with explicit attribution to **any Pfizer drug** that appear in the reviewed information must be recorded on the Case report form (CRF) and reported, within 24 hours of awareness, to Pfizer Safety using the NIS AEM Report Form.

- Scenarios involving drug exposure, including exposure during pregnancy, exposure during breast feeding, medication error, overdose, misuse, extravasation, lack of efficacy, and occupational exposure associated with the use of a Pfizer product must be reported, within 24 hours of awareness, to Pfizer Safety using the NIS AEM Report Form.

For these AEs with an explicit attribution or scenarios involving exposure to a Pfizer product, the safety information identified in the unstructured data reviewed is captured in the Event Narrative section of the report form, and constitutes all clinical information known regarding these AEs. No follow-up on related AEs will be conducted.

All the demographic fields on the NIS AEM Report Form may not necessarily be completed, as the form designates, since not all elements will be available due to privacy concerns with the use of secondary data sources. While not all demographic fields will be completed, at the very least, at least one patient identifier (e.g., gender, age as captured in the narrative field of the form) will be reported on the NIS AEM Report Form, thus allowing the report to be considered a valid one in accordance with pharmacovigilance legislation. All identifiers will be limited to generalities, such as the statement "A 35-year-old female..." or "An elderly male...". Other identifiers will have been removed.

Additionally, the onset/start dates and stop dates for "Illness", "Study Drug", and "Drug Name" may be documented in month/year (mmm/yyyy) format rather than identifying the actual date of occurrence within the month /year of occurrence in the day/month/year (DD/MMM/YYYY) format.

All research staff members must complete the following Pfizer training requirements:

- "YRR Training for Vendors Working on Pfizer Studies (excluding interventional clinical studies and non-interventional primary data collection studies with sites/investigators)".*

These trainings must be completed by research staff members prior to the start of data collection. All trainings include a "Confirmation of Training Certificate" (for signature by the trainee) as a record of completion of the training, which must be kept in a retrievable format. Copies of all signed training certificates must be provided to Pfizer.

Re-training must be completed on an annual basis using the most current Your Reporting Responsibilities training materials.

11. Plans for Disseminating and Communicating Study Results

In the event of any prohibition or restriction imposed (e.g., clinical hold) by an applicable competent authority in any area of the world, or if the investigator is aware of any new information which might influence the evaluation of the benefits and risks of a Pfizer product, Pfizer should be informed immediately.

This study aims to achieve quality results to be published in abstracts/posters at national and international scientific congresses and/or peer reviewed journals. The authors of all publications resulting from this study will be determined in accordance with the requirements of the International Committee of Medical Journal Editors (ICMJE), which states:

